## 7.1 Specification of Safety Parameters

We expect no adverse events based on prior research we’ve conducted. However, precautions will be taken to ensure patient safety as detailed above.

The imaging protocol used in this study includes only the minimum MR scanning needed to execute the tasks and paradigms for the research project. No report will be generated or supplied to the research participants. However, all scans performed for this project will be reviewed for gross abnormalities by a radiologist to be named prior to any subject enrollment. All research studies at SH have a radiologist assigned to read images. We will work with [name], Director for the Division of Radiology and Biomedical Engineering at MSU, and Medical Director of Adult Radiology at SH to assure similar processes are executed for our study. Moreover, our neuroimaging mentor [name] will provide oversight and has established relationships with the SH radiology team and will help ensure the safety of our participants and the clinical procedures. Although no diagnosis will be made, in the event that abnormal findings are identified, the investigator ([name]) will be informed and will assume responsibility for notifying the participants.

In the case that abnormal findings are identified, the participant’s physician (identified via the patient’s electronic medical record) will be contacted by the PI ([name]), or a designee of the PI (such as the research coordinator), and the findings will be reported. A report generated by the identified radiologist will be made available to the physician if requested.

For clinically significant findings of neuroimaging, the participant may choose to obtain appropriate clinical care or seek a second opinion. This might change the participant's insurability and employability as it relates to the clinical finding only. Seeking care may place the participant at risk for unforeseen medical costs, particularly for conditions that are benign. However, the presumption is that detection of a potentially clinically significant finding will prove to be beneficial. In the event of incidental findings, the neuroimaging mentor ([name]) will be consulted to determine if the abnormal finding precludes participation.

## 7.2 Methods and Timing for Assessing, Recording, and Analyzing Safety Parameters

We anticipate that ADAPT will be associated with low risk based on our prior research. In addition, we will carefully monitor for adverse events, including a specific form administered to participants (post-assessment, ADAPT session 2, and, for those completing ADAPT after the waitlist period, session 6.)

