#### **6.2.4 Adverse Event Queries/Additional Measures**

##### ADAPT Session 2:

Participants will be queried about any experienced adverse events during their second session of ADAPT (if randomized to ADAPT treatment group). This form will also be administered at post assessment. For those randomized to waitlist, they will complete this form at post assessment, ADAPT sessions 2 and 6 (if they opt to complete ADAPT).

- *Adverse Event Query Form.* A form to be completed via clinician interview assessing for adverse events experienced by participants.

##### ADAPT Session 6

During the last session of ADAPT, participants (in both the ADAPT treatment and waitlist control groups) will be queried as to whether they found the ADAPT intervention helpful when coping with distress related to COVID-19.

- *Child COVID-19 Related Distress Coping.* An item assessing whether the intervention was helpful in improving the child’s coping with distress in relation to the COVID-19 pandemic.

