## 7.3 Adverse Events and Serious Adverse Events

An **adverse event (AE)** is generally defined as any unfavorable and unintended diagnosis, symptom, sign (including an abnormal laboratory finding), syndrome or disease which either occurs during the study, having been absent at baseline, or if present at baseline, appears to worsen. Adverse events are to be recorded regardless of their relationship to the study intervention.

A **serious adverse event (SAE)** is generally defined as any untoward medical occurrence that results in death, is life threatening, requires inpatient hospitalization or prolongation of existing hospitalization, results in persistent or significant disability/incapacity, or is a congenital anomaly.

Adverse events and unanticipated problems will be carefully monitored and documented at each study visit. During all phases of the study (i.e., assessment and treatment), adverse events and unanticipated problems (whether or not they are thought to be study-related) will be monitored and documented in several ways.

1) During screening, assessments, and for those completing the ADAPT intervention, the interventionist ([name]) will maintain an individual log to record any increases in pain or mood-related problems during the study. [name] will review these logs each week.

2) In addition, the study team will have quarterly meetings to monitor the progress of the study, the integrity of the treatment, discuss the need for any protocol refinements, and conduct regular safety monitoring checks of adverse events and unanticipated problems. Severe depressive symptoms or active suicidal ideation will be recorded as an adverse event.

3) Any adverse events/unanticipated problems reported during the study including during the assessment (e.g., measures and fMRI/water loading) or during ADAPT sessions will be immediately brought to the attention of the study team. The IRB requires yearly renewal of study protocols, which provides additional monitoring of participant safety. The study team will review study data to ensure safety compliance and proper reporting to the IRB.

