### 9.4 Interim Analyses and Stopping Rules

There are no planned interim analyses. [name] will assess adherence and retention. If the treatment is deemed to be ineffective, unsafe, futile, or if there is evidence of poor study performance (e.g., slow accrual, high losses-to-follow-up, and poor quality control), a safety review may be warranted. This action would occur in consultation with the study mentors ([name], [name]), the IMC, and NCCIH. Examples of findings that might trigger a safety review are the number of SAEs overall, the number of occurrences of a particular type of SAE, severe AEs/reactions, or increased frequency of events. Such findings are presented to the study statistician ([name]) or to the IMC statistician to review the events by group to determine whether there are statistical as well as clinical concerns. The statistician reports his

findings to a closed session of the IMC or to the Safety Officer and/or NCCIH. The findings are used to determine what steps will be taken.

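### During the randomized period, adverse events are sought more often in ADAPT than in waitlist, so a by-group look at non-serious events is not like for like

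*Combined protocol and SAP*

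**What the plan says.** Section 6.2.4 sets the AE form for the ADAPT arm: "Participants will be queried about any experienced adverse events during their second session of ADAPT (if randomized to ADAPT treatment group"). It continues: "This form will also be administered at post assessment". For the other arm it says: "For those randomized to waitlist, they will complete this form at post assessment, ADAPT sessions 2 and 6 (if they opt to complete ADAPT"). Section 7.2 gives the same schedule, describing monitoring "including a specific form administered to participants (post-assessment, ADAPT session 2" and then session 6 for waitlist children who cross over. Section 7.4 and the schedule in 6.1 agree with this.

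The Précis and section 3 describe six weekly ADAPT contacts: two sessions, then four weeks of modules with interventionist support. No contact with waitlist families is described between baseline and post assessment. Section 7.3 adds that, at screening, at assessments and for children completing ADAPT, the interventionist "will maintain an individual log to record any increases in pain or mood-related problems during the study". The logs are reviewed weekly. Section 7.3 counts AEs whether or not they are related to the intervention, and includes worsening of what was present at baseline.

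Sections 6.2.3 and 9.2 have the study statistician prepare closed-session monitoring reports by Treatment A and B, and name a safety problem in one arm as a possible reason for full unblinding. Section 9.4 plans no interim analysis, but certain findings may trigger a safety review. Those findings go to a statistician "to review the events by group to determine whether there are statistical as well as clinical concerns". No time window is set for that look.

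**The concern.** These are anxious children with abdominal pain, so background worsening of pain or mood is likely and counts as an AE. An arm that is asked more often will have more of these events on record, even if the true risk is equal. One trigger named in section 9.4 is a rise in the frequency of events, which unequal asking can itself produce.

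Two errors are possible. An apparent ADAPT excess could prompt a safety review or unblinding without cause. Conversely, events in waitlist children between baseline and post assessment could go unrecorded, so that a true waitlist excess is hidden. Nothing in 7.2 or 9.4 warns the statistician or the monitoring committee that the arms were observed differently.

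**Working it through.** The plan states no AE rate, recall probability or safety boundary, so there is no figure of its own to reproduce. Section 7.1 says that no adverse events are expected.

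**Count of scheduled forms**

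| | ADAPT | Waitlist |
|---|---|---|
| Randomized period | 2 (session 2, post) | 1 (post) |
| Whole study, if waitlist child opts into ADAPT | 2 | 3 (post, sessions 2 and 6) |
| Weekly interventionist contacts before post assessment | 6 | none described |

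**Extra form alone.** Assume events are spread evenly over about seven weeks: six weeks of treatment or waitlist (section 3) plus about one week to the post visit (6.2.5). Let f be the share of events before session 2. Let r be the chance that such an early event is recalled at the post visit. Assume later events are recalled with probability 0.9 and early ADAPT events are fully captured at session 2. Then:

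- waitlist capture = f × r + (1 − f) × 0.9
- ADAPT capture = f + (1 − f) × 0.9

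| f | r | Waitlist | ADAPT | Ratio |
|---|---|---|---|---|
| 1/7 | 0.8 | 0.886 | 0.914 | 1.03 |
| 1/7 | 0.5 | 0.843 | 0.914 | 1.08 |
| 2/7 | 0.8 | 0.871 | 0.929 | 1.07 |
| 2/7 | 0.5 | 0.786 | 0.929 | 1.18 |

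For scale, take 20 children per arm and an assumed true risk of 40%, so 8 affected children per arm. The expected gap in recorded cases is 8 × (0.914 − 0.886) = 0.2 at the low end and 8 × (0.929 − 0.786) = 1.1 at the high end.

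**Second model, to see what contacts and logs could add.** Let q be the chance that the post form alone captures an event. Extra ascertainment covers a share f of events and picks up 90% of those that the post form would miss. ADAPT capture is q + f × 0.9 × (1 − q), and waitlist capture is q.

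- Form only, f from 1/6 to 2/7: ratio 1.15 to 1.26 at q = 0.5, and 1.04 to 1.06 at q = 0.8.
- Contacts and log covering all events, f = 1: 0.95/0.5 = 1.90 at q = 0.5, and 0.98/0.8 = 1.23 at q = 0.8.
- If q = 1, the ratio is 1.00.

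**Chance of a false signal** (exact binomial enumeration, 20 per arm, equal true risk of 40%, Fisher p < 0.05 against ADAPT)

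| Ascertainment | q = 0.5 | q = 0.8 |
|---|---|---|
| Extra form only (f = 2/7) | 2.9% | 1.8% |
| Form plus weekly contacts and log (f = 1) | 15.8% | 3.8% |

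With equal and full ascertainment the figure is 1.2%. The f = 1 row is an upper case, because it supposes that every event is open to capture at some contact.

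**The case against.** A reader might infer that the trial plans a safety comparison and that it is biased against ADAPT throughout. The documents do not support that.

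- The section 9.4 review is conditional. There is no planned interim analysis, no test and no boundary, and the findings go for judgement to a closed committee session, the safety officer or the funder.
- Most triggers listed there are serious or severe events, which depend less on how often one asks.
- The direction holds only in the randomized period. A waitlist child who crosses over gets three forms, and is followed for about 16 weeks against about 10 in ADAPT. If events after crossover were counted under waitlist, the imbalance could reverse.
- Waitlist children are not unobserved. The log also covers screening and assessments, and spontaneous reports count in both arms.
- The magnitude rests wholly on assumptions, and for the form alone it is modest.

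All of this stands, and it limits the point to non-serious events in the randomized period. It does not remove it: the form count is explicit, by-group reporting exists, and no time window or caution is given.

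A reader might also infer that the by-group review should be confined to the post-assessment form plus serious events. That would do harm. Section 8 says that worsening distress and pain lead to discontinuation, and that children who discontinue are unlikely to be retained for later assessments. Their events may be known only from session 2 or the log. Severe events that do not meet the serious definition would also drop out. Nor is the post form alone clearly equal between arms: no recall window is stated, and a child already asked at session 2 may not repeat an event.

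**Conclusion.** The point holds in a limited form. Up to post assessment, ADAPT has two AE forms, six weekly contacts and a session log, against one form in waitlist. Any by-group look at non-serious events in that period can therefore differ between arms for reasons of ascertainment alone, provided that the single post-assessment query misses some events. Serious events are less exposed.

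The extra form alone gives a ratio of about 1.03 to 1.18, if early events are recalled 50% to 80% of the time, later ones 90%, and 1/7 to 2/7 of events fall before session 2. Contacts and logs could raise this, but by how much cannot be derived from the documents. The plan does not establish a bias against ADAPT over the whole study, because section 9.4 sets no window. This is a cheap improvement to the safety reporting, not a flaw in the efficacy analysis.

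**What to change.** **In 6.2.4 and 7.2:** give waitlist families the same AE query at the week that matches ADAPT session 2, by phone, video or the existing REDCap link. The form is a clinician interview, so phone or video is the closer match. Handle it so that the blinded outcome assessor does not learn the assignment.

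**In 9.4, and for the A/B monitoring reports:** limit the by-group comparison to the randomized period. Report time at risk by arm, since the ADAPT sessions may take up to eight weeks against a six-week waitlist. Show two tables side by side:

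- (a) events from query points common to both arms, as the like-for-like comparison;
- (b) all events from any source, including serious events, severe events, and session or log events in children who discontinue, with the source labelled.

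Remove no event from the safety review. Report events after crossover separately.

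**Cost:** one short extra query per waitlist family, one extra table, and a few sentences in these sections. With the matched query, the forms contribute a ratio of 1.00 under equal true risk and equal recall. The contacts and log still differ between arms, which is why table (b) needs its source labels.

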## 7.3 Adverse Events and Serious Adverse Events

An **adverse event (AE)** is generally defined as any unfavorable and unintended diagnosis, symptom, sign (including an abnormal laboratory finding), syndrome or disease which either occurs during the study, having been absent at baseline, or if present at baseline, appears to worsen. Adverse events are to be recorded regardless of their relationship to the study intervention.

A **serious adverse event (SAE)** is generally defined as any untoward medical occurrence that results in death, is life threatening, requires inpatient hospitalization or prolongation of existing hospitalization, results in persistent or significant disability/incapacity, or is a congenital anomaly.

Adverse events and unanticipated problems will be carefully monitored and documented at each study visit. During all phases of the study (i.e., assessment and treatment), adverse events and unanticipated problems (whether or not they are thought to be study-related) will be monitored and documented in several ways.

1) During screening, assessments, and for those completing the ADAPT intervention, the interventionist ([name]) will maintain an individual log to record any increases in pain or mood-related problems during the study. [name] will review these logs each week.

2) In addition, the study team will have quarterly meetings to monitor the progress of the study, the integrity of the treatment, discuss the need for any protocol refinements, and conduct regular safety monitoring checks of adverse events and unanticipated problems. Severe depressive symptoms or active suicidal ideation will be recorded as an adverse event.

3) Any adverse events/unanticipated problems reported during the study including during the assessment (e.g., measures and fMRI/water loading) or during ADAPT sessions will be immediately brought to the attention of the study team. The IRB requires yearly renewal of study protocols, which provides additional monitoring of participant safety. The study team will review study data to ensure safety compliance and proper reporting to the IRB.

## **7.4 Reporting Procedures**

Case report forms for AEs and SAEs have been developed. An AE documentation form will be completed by a clinician at the second ADAPT session and during the post assessment. For those randomized to waitlist control who are completing ADAPT after the post assessment, they will complete this information during session 2 and 6 of ADAPT in addition to the post-assessment query. The form documents whether or not an adverse event has occurred and throughout the trial if any AEs/SAEs are spontaneously reported by participants. AEs will be reported by body system and rated by level of severity (mild, moderate, severe, life-threatening). The primary study team will meet regularly to monitor the progress of the study and safety of participants in blinded fashion. Reportable events will also be recorded in a separate study database.

For any adverse event meeting the definition of “severe” or “life threatening,” the study interventionist ([name]) and research coordinator will communicate with one another to complete a “Serious Adverse Event” reporting form within one working day. Any severe or life threatening adverse event report will be sent to the IMC and the IRB will be notified.

To satisfy the requirement for prompt reporting, unanticipated problems will be reported using the following timeline:

- Unanticipated problems that are serious adverse events will be reported to the IRB, Independent Safety Monitor(s), and NCCIH within 7 days of the investigator becoming aware of the event.
- Any other unanticipated problem will be reported to the IRB, Independent Safety Monitor(s), and NCCIH within 14 days of the investigator becoming aware of the problem.

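### Section 7.4 triggers the SAE form and the IMC/IRB notice by severity grade, while section 7.3 defines an SAE by outcome, so the two can disagree in both directions.

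*Combined protocol and SAP*

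**What the plan says.** Section 7.3 defines an SAE by what happens to the participant. Besides death and threat to life, an event is serious if it "requires inpatient hospitalization or prolongation of existing hospitalization, results in persistent or significant disability/incapacity, or is a congenital anomaly". Severity plays no part in that definition.

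Section 7.4 has adverse events "rated by level of severity (mild, moderate, severe, life-threatening"). An event in the top two grades leads to completion of a Serious Adverse Event "reporting form within one working day". The next sentence sets the notice: "Any severe or life threatening adverse event report will be sent to the IMC and the IRB will be notified". Neither sentence refers to 7.3.

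One rule in 7.4 does use seriousness, but only jointly with a second condition: "Unanticipated problems that are serious adverse events will be reported to the IRB, Independent Safety Monitor(s), and NCCIH within 7 days". Other unanticipated problems go to the same three bodies within 14 days. Section 7.6 sends significant study-related or unanticipated events to the IRB and sponsor, and reportable events to the IRB immediately.

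Section 9.4 says that "a safety review may be warranted" and gives example triggers: "the number of SAEs overall, the number of occurrences of a particular type of SAE, severe AEs/reactions, or increased frequency of events". The statistician then reports "findings to a closed session of the IMC or to the Safety Officer and/or NCCIH".

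**The concern.** Seriousness and severity are different properties. A short precautionary admission can be serious but only moderate in intensity; an intense symptom that resolves at home can be severe but not serious. Section 7.4 uses the second property to drive a form and a notice that belong to the first.

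Two things are at stake. The first is whether the IMC, as the independent safety body, sees each SAE individually. Take a hypothetical child who vomits after the water load, is admitted overnight, and has the event graded moderate. The admission meets 7.3. Section 7 lists vomiting as a risk of the task, yet its risk/benefit paragraph and section 7.1 say adverse events are not expected, so the event could be judged anticipated or not. If it is judged anticipated, no SAE form and no individual IMC report is required. *Unanticipated problem* is not defined in the documents.

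The second is the SAE count in 9.4. The section does not say whether it counts events meeting 7.3 or forms completed under 7.4. The reverse mismatch is also plausible: 7.3 has severe depressive symptoms recorded as an adverse event, and if such an event is graded severe it goes on an SAE form without necessarily meeting any 7.3 criterion.

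**Working it through.** The plan states no figure to reproduce, so the check sets the rules side by side.

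**Step 1: the combinations.** Cross seriousness under 7.3 (2 levels), grade under 7.4 (4) and unanticipated problem (yes/no): 2 × 4 × 2 = 16. A life-threatening event is serious by definition, so the 2 non-serious, life-threatening combinations are impossible. That leaves 16 − 2 = 14: 8 serious and 6 non-serious.

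**Step 2: apply the rules of 7.4.**

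| 7.3 status | Grade | Unanticipated problem | Combinations | SAE form | Individual report to IMC or monitors |
|---|---|---|---|---|---|
| SAE | severe or life-threatening | either | 4 | yes | yes |
| SAE | mild or moderate | yes | 2 | no | yes (7 days) |
| SAE | mild or moderate | no | 2 | no | none required |
| Not SAE | severe | either | 2 | yes | yes |
| Not SAE | mild or moderate | yes | 2 | no | yes (14 days) |
| Not SAE | mild or moderate | no | 2 | no | none required |

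- SAE without an SAE form: 2 + 2 = 4 of 8.
- Non-serious event with an SAE form: 2 of 6.
- Form disagrees with the definition: 4 + 2 = 6 of 14.
- SAE with no required individual report to the IMC or monitors: 2 of 8.

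These are combinations of rules, not event frequencies.

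**Step 3: look for another route to the IMC.** Three individual reports are required: the 7.4 severity notice, the 7-day rule and the 14-day rule. None applies to an SAE graded mild or moderate that is not an unanticipated problem. Three further routes may reach the IMC: the 9.4 safety review, the closed-session monitoring reports (6.2.3 and the Blinding part of 9.2), and data supplied on request (Table 1). They are aggregate, discretionary or on request, and have no time limit. The routes in 7.6 name the IRB and sponsor, not the IMC; 7.3 brings all events to the study team.

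**Step 4: which criteria are exposed in practice.** Life-threatening is itself a 7.4 trigger. A death would presumably be graded at the top, although the scale has no fatal grade. Congenital anomaly is unlikely because 4.2 excludes pregnancy. Hospitalisation and disability or incapacity remain.

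**Step 5: likely frequency.** The only event rate given is in section 7: 1 child in 230 vomited in the study that validated the water load. Assuming one load per child there, 1/230 = 0.43%, with an exact 95% interval of 0.01% to 2.40%. Section 4 allows 34 to 50 completed participants, each with two loads:

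- 2 × 34 = 68 loads: 68 × 1/230 = 0.30 vomiting events expected (0.01 to 1.63).
- 2 × 50 = 100 loads: 100 × 1/230 = 0.43 expected (0.01 to 2.40).

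Vomiting is not in itself an SAE, and admissions would be fewer. No admission or SAE rate is given.

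**The case against.** The strongest reply has four parts.

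*Section 7.4 says when a form is required, not that other SAEs get none.* It mentions that AE and SAE forms exist, and the revision history ties the forms to set time points. This is fair as far as it goes: the text does not forbid a form. But it gives no trigger for one either, and a procedure that leaves this to initiative does not assure it.

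*The definition of severe is not shown and might cover hospitalisation.* It might, in which case the gap would shrink or close. The documents refer to such a definition without giving it, and place the word in a plain intensity scale, so this cannot be relied on.

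*Severe may simply have been written for serious.* The title of the form and the wording of the revision history support this. Against it, 7.4 uses the serious category correctly a few lines later, and 9.4 lists SAEs and severe events separately. On either reading the operative sentence needs correcting.

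*The remaining gap is small.* This stands. The IRB is likely to hear of a study-related admission through 7.6. Many SAEs could go to the monitors as unanticipated problems, since the protocol expects no adverse events. The two combinations in which a non-serious event gets an SAE form err towards over-reporting. It is also natural to read the 9.4 count as using 7.3, though it does not say so. What no route supplies is a required individual report to the IMC for the residual class.

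**Conclusion.** The concern holds. The trigger in 7.4 does not match the definition in 7.3: the SAE form disagrees with it in 6 of 14 rule combinations, and 2 of 8 SAE combinations carry no required individual report to the IMC. The practical gap is a hospitalisation or disability graded mild or moderate and judged not to be an unanticipated problem. It should be rare in a trial of this size.

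This is not a claim about delay. The one-working-day limit covers completing the form; the severity-based notice has no time limit for sending to the IMC.

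The count rests on two assumptions that favour the protocol and that the documents do not confirm: that the Independent Safety Monitor(s) in 7.4 are the IMC, and that the closed sessions in the blinding text are the IMC's. It also takes 7.4 literally, without the unseen definition of severe. The point should be corrected because it sits in an operative safety rule and is cheap to repair; it does not bear on the efficacy analysis.

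**What to change.** Reconcile 7.3, 7.4 and 9.4:

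- In 7.4, trigger the SAE form and the IMC/IRB notice for any event that meets the 7.3 definition, whatever its grade.
- Keep the existing IMC/IRB notice for severe or life-threatening events.
- Record seriousness and severity as separate items, if the forms (not included in the documents) do not already do so.
- State in 9.4 that the SAE count uses the 7.3 definition.
- If *severe* was meant as *serious*, correct the word in 7.4.

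The cost is one or two sentences in 7.4, one in 9.4, and a form field only if it is missing. The IMC may receive a few more reports. No existing notice is removed.
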